	antifibrotic treatment between October 1, 2014 and April 30, 2018. Patients will be divided into three mutually exclusive cohorts: (1) nintedanib initiators; (2) pirfenidone initiators; and (3) control cohort who received no prescription antifibrotic treatment during selection window.										
Variables:	The following demographic and clinical characteristics as well as medical interventions for IPF during the 12-month baseline period (pre-treatment) will be evaluated and compared between cohorts 
 Demographic characteristics (e.g., age, gender, race/ethnicity, geographic region, insurance type) Clinical characteristics (e.g., selected comorbidities, baseline weight and body mass index [BMI], blood pressure, smoking status, laboratory measures, pulmonary function tests) Pharmacological interventions (e.g., index medication dose, time from the earliest diagnosis of IPF to index medication, other IPF treatments, bronchodilators, corticosteroids) Non-pharmacological interventions (e.g., surgical procedures, supportive therapies, diagnostic procedures) 										
Data sources:	GE Centricity EMR database from October 2013 to April 2018										
Study size:	A preliminary analysis identified 868 IPF patients with pirfenidone, 615 patients with nintedanib, and about 10,000 untreated patients.										
Data analysis:	Patient demographic and clinical characteristics will be described using descriptive analyses. Counts and percentages for categorical variables and measures of central tendency (mean, median, standard deviation [SD], and min/max) for continuous variables will be reported. Differences between the treatment cohorts (compared to each other and to untreated patients) will be assessed using absolute standardized differences and p-values. The probabilities of receiving one treatment over another will be tested by propensity scores and using multivariable logistic regression adjusted for key baseline characteristics. The similarities and differences between two treatment cohorts will be assessed using balance diagnostics tests. A stratified descriptive analysis will also be conducted at different time points to assess if the characteristics of the two exposures changes over time.										

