9.3 VARIABLES

9.3.1 Exposures

Both nintedanib (Ofev, BI) and pirfenidone (Esbriet, Genentech) were approved by the US FDA on October 15, 2014 (reflected by start of selection window in this study). Nintedanib initiators will be identified using prescription records for nintedanib, with the index date being the first prescription in the EMR during the selection window. Similarly, pirfenidone initiators will be identified using prescription records for pirfenidone; index date is first prescription. New users of these medications will be selected into the study, excluding those who initiated both medications on index. The number of patients who initiated both medications on index will be reported during the patient attrition. Since the purpose of this study is to identify predictors of IPF treatment initiation, no post-index follow-up measures will be reported. Patients who switched between the treatments during the pre-index period will be excluded because of the new user design, and those who switch after the index date will not be a concern as no study measures will be evaluated during the post-index period for the objectives of this study. No validation will be performed on the exposures of interest as exposure ascertainment relies on evidence of ≥ 1 prescription record.

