9.3.2 Outcomes

9.3.2.1 Primary outcomes

The primary outcome will be the ASD and p-value comparing baseline patient characteristics (as described in section 9.3.3) between the following cohorts:

- Nintedanib vs. pirfenidone
- Nintedanib vs. untreated
- Pirfenidone vs. untreated

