9.3.3 Covariates

The following measures will be evaluated during the 12-month baseline period, including index date, unless otherwise noted. Measures will be reported separately for each of the three cohorts.

For nintedanib and pirfenidone cohorts only:

- Index medication (n, %)
 - Nintedanib
 - Pirfenidone
- Average daily dose of the index prescription
 - Nintedanib (mean, SD, median, min, max) and categories (n, %)
 - 100 mg
 - 150 mg
 - Unknown
 - Pirfenidone (mean, SD, median, min, max) and categories (n, %)
 - 267 mg
 - Unknown
- Time from the earliest diagnosis for IPF to index (mean, SD, median, min, max)
- Prescribing physician specialty (n, %)
 - Primary care
 - Internal medicine
 - Pulmonologist
 - Other

For all cohorts:

Demographic characteristics

- Age (mean, SD, median, min, max) and age categories on index date (n, %)
 - 40-49
 - 50-59

- 60-69
 - ≥ 70
- Gender (n, %)
 - Male
 - Female
- Index year (n, %)
 - 2014
 - 2015
 - 2016
 - 2017
 - 2018
- Region (n, %)
 - Northeast
 - Midwest
 - South
 - West
- Race/ethnicity (n, %) (expected to be missing for about 40% of patients)
 - White
 - African American
 - Hispanic
 - Asian
 - Other
 - Unknown
- Payer type (n, %)
 - Commercial
 - Medicaid
 - Medicare
 - Self-Insured
 - Other/Unknown

Clinical characteristics (based on ICD-9/10-CM procedure and diagnosis codes, laboratory test codes, CPT codes and NDC/RxNorm (to be included in Appendix), as well as other information in the EMR encounter files)

- Body weight (lbs; mean, SD, median, min, max)
 - Body mass index (BMI; kg/m²; mean, SD, median, min, max)
 - BMI category, defined using BMI field (n, %)
 - Underweight ($<18.5 \text{ kg/m}^2$)
 - Normal weight (18.5 to 24.99 kg/m²)
 - Overweight (25 to 29.99 kg/m²)
 - Obese (30 to 34.99 kg/m²)
 - Very obese ($\geq 35 \text{ kg/m}^2$)

- Blood pressure (BP)¹⁴ (n, %)
 - Diastolic BP
 - Normal (<80 mmHg)
 - High (≥ 80 mmHg)
 - Systolic BP
 - Normal (<120 mmHg)
 - Elevated (≥ 120 and < 129 mmHg)
 - High (≥ 130 mmHg), further broken down as follows if data allow
 - Stage 1 (≥ 130 and < 139 mmHg)
 - Stage 2 (≥ 140 mmHg)
- Smoking status at index (n, %); excluding smokeless tobacco; categories to be finalized during analysis
 - Smoker
 - Non-smoker, further broken down as follows if data allow
 - Previous smoker
 - Never smoker
 - Unknown/missing
- Alcohol consumption (n, %)
 - Yes
 - No
 - Unknown/missing

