 - Carbon monoxide diffusing capacity of the lung (DLCO; n, %)

- Normal (>75% of predicted)
- Mild to moderate decrease (40-74% of predicted)
- Severe decrease (<40% of predicted)
- Oxygen saturation (n, %)
 - Normal (95-100%)
 - Below normal (<95%)
- GAP index¹⁸ (n, %), if data allow
 - Calculated using information on age, gender and FVC
 - Stage I (0-3 points)
 - Stage II (4-5 points)
 - Stage III (6-8 points)

Treatment history during the pre-index period (not including index date):

- Pharmacological interventions (n, %)
 - Other treatments (as per ATS/ERS/JRS/ALAT guidelines¹⁹)
 - Selective tyrosine kinase inhibitor against platelet derived growth factor (Imatinib)
 - Prednisone
 - Azathioprine
 - N-acetylcysteine
 - Selective endothelin receptor antagonist (ambrisentan)
 - Phosphodiesterase-5 inhibitor (sildenafil)
 - Dual endothelin receptor antagonists (macitentan, bosentan)
 - Corticosteroids
 - Inhaled corticosteroids
 - Oral corticosteroids
 - Bronchodilators
 - SABA
 - LABA
 - Anticholinergics
 - Other beta agonists
 - GERD therapy
 - H-2 receptor blockers
 - Proton pump inhibitors
 - Antacids
 - Cardiovascular drugs
 - Antianginals
 - Antihypertensives
 - Antiarrhythmics
 - Antiplatelets
 - Anticoagulants

- Antidiabetes drugs
- Anti-infectives
- Anticonvulsants
- Anti-anxiety drugs
- Antidepressants
- Antipsychotics
- Antihyperlipidemics
- Non-pharmacological interventions (n, %)
 - Surgical procedures (n, %)
 - Lung transplantation
 - Esophageal sphincter reinforcement
 - Lung cancer surgeries
 - Supportive therapy (n, %)
 - Oxygen therapy
 - Pulmonary rehabilitation
 - Diagnostic procedures (n, %)
 - High resolution computed tomography (HRCT)
 - Surgical lung biopsy
 - Chest X-rays
 - 6-minute walk test/pulmonary stress test
 - Spirometry
 - Bronchoalveolar lavage

Treatment on the index date (pharmacological interventions only):

- For each of the following treatments, the number and proportion of patients with and without the treatment on the index date will be reported (days' supply to be considered when exploring treatment use on index)
 - Other treatments (as per ATS/ERS/JRS/ALAT guidelines¹⁹; n, %)
 - Selective tyrosine kinase inhibitor against platelet derived growth factor (Imatinib)
 - Prednisone
 - Azathioprine
 - N-acetylcysteine
 - Selective endothelin receptor antagonist (ambrisentan)
 - Phosphodiesterase-5 inhibitor (sildenafil)
 - Dual endothelin receptor antagonists (macitentan, bosentan)
 - Corticosteroids (n, %)

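### Drugs recorded on the index date are in the primary comparison and eligible for the models, so a drug co-prescribed because an antifibrotic was started can be flagged as a driver of that choice

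*Combined protocol and SAP*

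**What the plan says.** Section 9.3.3 contains two drug blocks listing the same classes, both for all cohorts ("Measures will be reported separately for each of the three cohorts").

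- The first is headed "Treatment history during the pre-index period (not including index date").
- The second covers drug treatment on the index date: "the number and proportion of patients with and without the treatment on the index date will be reported". Its only rule on timing is "days' supply to be considered when exploring treatment use on index".

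Under Section 9.2 the treated index date is the first antifibrotic prescription. The untreated index date is the earliest IPF diagnosis or a randomly assigned date.

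The primary outcome in Section 9.3.2.1 is the ASD and p-value "comparing baseline patient characteristics (as described in section 9.3.3) between the following cohorts", with no exception for the index-date block. Section 9.7.1 says the p-values help identify key drivers of treatment selection, and it selects model covariates on bivariate significance or face validity, possibly stepwise. Section 9.3.1 gives the reading intended for the results: "Since the purpose of this study is to identify predictors of IPF treatment initiation".

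The timing statements differ. The abstract refers to "medical interventions for IPF during the 12-month baseline period (pre-treatment) will be evaluated and compared between cohorts". Section 9.2 starts the post-index period at the index date and says no study measures are assessed in it. Section 9.3.3 opens with "The following measures will be evaluated during the 12-month baseline period, including index date, unless otherwise noted".

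**The concern.** On a treated patient's index date, two kinds of drug record can appear. Some drugs were already in use and could have influenced the choice of antifibrotic. Others may have been written at the same visit because the antifibrotic was being started. The index-date block puts both into one yes/no variable.

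Only the first kind can be a predictor of initiation. If the second kind produces a difference between cohorts, the plan would flag it by ASD or p-value, could admit it to the propensity and logistic models, and would interpret it as something that drives initiation. The study's central reading, which characteristics lead to nintedanib, pirfenidone or no treatment, would then be wrong for that drug class.

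**Working it through.** **Route through the plan.** (1) The index-date block holds 28 drug lines in 12 groups: 7 other treatments, 2 corticosteroid, 4 bronchodilator, 3 GERD, 5 cardiovascular and 7 single classes (7 + 2 + 4 + 3 + 5 + 7 = 28). (2) It sits in Section 9.3.3, so Section 9.3.2.1 compares it. (3) Section 9.7.1 uses the resulting p-values to identify drivers. (4) The same section makes significant variables eligible for the models. (5) No sentence limits the block to description or separates same-day new prescriptions from ongoing use.

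**Size.** The plan states no figure on this point, so there is none to reproduce. What follows is illustrative.

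Inputs from the documents:
- preliminary counts of 615 nintedanib, 868 pirfenidone and about 10,000 untreated patients (Abstract), hence 615 + 868 = 1,483 treated; Table 1 warns that counts will change once the criteria are applied
- ASD threshold 0.10 and two-sided alpha 0.05 (Section 9.7.1)

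Assumed: prior use p is identical in both cohorts, and a share c of prior non-users in one cohort starts the drug on the index date. Observed use there is x = p + c(1 − p).

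Formulas: ASD = |x − p| / √{[x(1 − x) + p(1 − p)]/2}, as in Section 9.7.1; p-value from a pooled two-proportion z test.

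*Nintedanib vs pirfenidone, prior use 10%, excess in the pirfenidone cohort:*
- x = 13.2% (c = 3.2/90 = 3.6%): ASD = 0.032/0.3198 = 0.100; z = 0.032/0.01705 = 1.88, p = 0.061. This reaches the ASD threshold but not p < 0.05.
- x = 14.5% (c = 4.5/90 = 5%): ASD = 0.045/0.3271 = 0.138; z = 0.045/0.01751 = 2.57, p = 0.010. This passes both. With the excess in nintedanib instead, p = 0.008 and the power to reach p < 0.05 is about 75%.

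*Comparisons with untreated patients: smallest excess, in percentage points, giving p < 0.05:*

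| Prior use | Nintedanib (615 vs 10,000) | Pirfenidone (868 vs 10,000) | All treated (1,483 vs 10,000) |
|---|---|---|---|
| 5% | 1.8 | 1.5 | 1.2 |
| 10% | 2.5 | 2.1 | 1.7 |
| 20% | 3.3 | 2.8 | 2.2 |
| 30% | 3.7 | 3.2 | 2.5 |

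In the last column the ASD is only about 0.05. These differences would be flagged by p-value, which is a route into the model, but not by ASD.

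**Using pre-index prescriptions only.** In every scenario the expected ASD is 0, and p < 0.05 arises at about the 5% chance rate per variable.

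**The case against.** The index-date sentence promises only reporting. Model entry is optional: covariates may be chosen on face validity, stepwise selection is only possible, and Section 9.9 expects some covariates to be left out for missing data. A reader might infer that the plan builds reversed cause and effect into the propensity models. The documents do not support that; they allow it and do not guard against it.

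Nor do they say that any supply covering the index date counts. The days'-supply wording is open and could be implemented to detect ongoing use only. The gap is an unspecified rule rather than a wrong one.

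The history block that excludes the index date is reported alongside, so a reader can see whether an index-date difference has a pre-index counterpart. This is real mitigation, but it does not stop the index-date variable from being tested and flagged.

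If both antifibrotics prompt the same co-prescribing and prior use is equal, there is no bias between them. That condition stands. All rates above are assumed, and the smallest scenario does not reach p < 0.05.

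The conflict with the abstract's pre-treatment label is weak taken alone, because the same entry lists index medication dose. The conflict between Sections 9.2 and 9.3.3 is firmer.

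**Conclusion.** The concern holds in a limited form. As written, the plan sends index-date drug use into the primary comparison and the search for drivers, and leaves it eligible for the models, without separating drugs already in use from those first written that day.

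Nintedanib vs pirfenidone is affected only if same-day starts differ between the two drugs. Under the equal-prior-use assumption at a 10% base, an excess of about 3 points reaches the ASD threshold and 4.5 points passes both criteria.

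Treated vs untreated is more exposed. Every treated index date is a prescribing date, whereas an untreated one may be a random day on which no record is required. With 1,483 vs 10,000 patients, 1.2 to 2.5 points on bases of 5% to 30% is enough for p of about 0.05.

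The documents cannot show how often this would happen, because they give no co-prescribing rates. It is an inexpensive improvement to make before analysis and does not invalidate the design.

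**What to change.** - State in Sections 9.3.2.1 and 9.7.1 that the driver comparison, the propensity scores and the logistic models use only drug exposure from prescriptions written before the index date: either the existing history block, or supply from such prescriptions that covers the index date.
- Keep the index-date block as description, in three parts: ongoing use from earlier prescriptions; same-day renewals in patients with any earlier prescription of that class; and first-ever same-day starts. The middle group is needed because an earlier user whose recorded supply has lapsed would otherwise fit nowhere.
- Reconcile the Abstract, Section 9.2 and Section 9.3.3 on whether the index date belongs to baseline. The answer also governs diagnoses and laboratory values, which Section 9.3.3 currently counts on that date by default.

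The cost is protocol wording and a date condition in the programming. A few drugs needed at the index visit for unrelated reasons would leave the driver analysis, but they would still be reported.

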9.4 DATA SOURCES

GE Centricity EMR database will be used for this study. This is an anonymized Health Insurance Portability and Accountability Act of 1996 (HIPPA) compliant database populated with patient data from ambulatory care records. The EMR database is obtained from a national network of primary care practices (through GE Centricity EMR System) whose providers allow their de-identified patient-level data to be available for research. Clinical data are captured from more than 725 member institutions, more than 43,000 providers and currently captures activity on over 42 million patients from 48 states & the District of Columbia. The EMR had 42 million active patients as of January 2018 and the data continues to grow. Of special interest for this study, there are about 456 Pulmonologist providing their patient data. Additionally, there are about 78 million records from patients covered by Medicare, 69 million from Medicaid, and 58 million records from commercially insured patients.

The size and geographic representation of the data network are illustrated in Figure 2.

Figure 2. Geographic representation of

GE Centricity EMR Database

At the individual patient-level, data are processed to provide researchers with demographic information, clinical characteristics (International Classification of Diseases, Ninth Revision, Clinical Modification (ICD-9-CM) and ICD-10 based medical diagnoses, patient complaints), diagnostic tests/results, procedures, insurance information (commercial, Medicare, Medicaid, etc.), and prescription details. Information from specialty healthcare providers (e.g., endocrinologists), and laboratory test orders/results are also available. The data are organized by practice and provide longitudinal medical records for each patient. Comparisons of the EMR patient population to the general population of the United States on demographics (US Census), outpatient visits related to acute and chronic conditions (NCHS-NAMCS), and disease prevalence (NCHS-NHANES) show the EMR is reflective of the US population receiving healthcare in the ambulatory setting.^{20,21}

The medical record in the EMR database provides patient level information including the following key analysis variables:

- Age
- Gender
- Race/ethnicity
- Geographic region
- BMI, height, weight
- Systolic BP, Diastolic BP, Pulse

- Procedures performed in outpatient settings (e.g. HRCT, SLB, chest X-rays, spirometry)
- Laboratory values, when recorded (e.g. anticoagulant test, blood counts, kidney and liver function tests)
- Behavioral measures (e.g. smoking status)
- Prescribing physician specialty
- Health insurance details
- Comorbid conditions
- Concomitant medication usage
- Outpatient encounters

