9.7.1 Main analysis

For the primary objective, baseline patient characteristics will be described using descriptive analysis, i.e. described as counts and percentages for categorical variables (e.g. gender, race, comorbidities, treatments, diagnostic tests performed) and measures of central tendency (mean, median, SD, and min/max) for continuous variables (e.g., age, lab measures values, BMI). Differences between the cohorts will be assessed using ASD, where an ASD of at least 10% will be considered a meaningful difference.²² Patients with missing data will be reported as missing and excluded from the comparison for the missing variable.

For continuous variables, the standardized differences will be calculated as

$$d = \frac{(\bar{X}_1 - \bar{X}_2)}{\sqrt{\frac{s_1^2 + s_2^2}{2}}}$$

Where \bar{X} denote sample means in each exposure cohort, and s denotes sample variances.

For categorical variables, the standardized differences will be calculated as

$$d = \frac{(p_1 - p_2)}{\sqrt{\frac{[p_1(1 - p_1) + p_2(1 - p_2)]}{2}}}$$

Where p denotes proportion of a binary baseline variable in the two exposure cohorts.

The confidence intervals (CIs) for standardized differences will also be calculated as defined below:

$$95\% CI = d \pm 1.96 \times \sigma [d]$$

$$\text{where, } \sigma [d] = \sqrt{\frac{n_1 + n_2}{n_1 \times n_2} + \frac{d^2}{2(n_1 + n_2)}},$$

Where n_i denotes sample sizes of each exposure cohort.

Bivariate statistical significance tests such as Chi-square test for categorical variables and Wilcoxon rank sum test or t-test for continuous variables (depending on distribution of data) will also be performed to compare differences in baseline characteristics between the three cohorts. In addition to standardized differences, p-value in comparing characteristics between the three cohorts will also be reported to help identify “key drivers” associated with treatment selection.

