For the second objective, the probabilities of receiving one treatment over another (or nintedanib or pirfenidone vs. untreated) will be tested by propensity scores (PS) and using multivariable logistic regression (possibly with stepwise selection) after controlling for key baseline characteristics (selected based on significance in bivariate analysis or face validity, e.g. age). The similarities and differences between the exposure cohorts will be assessed using balance diagnostics tests (e.g., graphical distribution of overlap between propensity scores of two cohorts (histograms, boxplots), percentage of sample matched, Pearson’s correlation coefficient, standardized differences, density estimates, c-statistics, receiver operating characteristic [ROC] curves). Ninety-five percent confidence intervals will be calculated for key parameters. Statistical tests will be two-sided, with α -level of 0.05 for statistical significance.

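### All intervals, tests and models treat patients as independent although records are grouped by practice; where both treatment choice and a characteristic cluster by practice, precision is overstated and practice differences can pass for patient-level drivers

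*Combined protocol and SAP*

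**What the plan says.** Section 9.4 describes the source as "more than 725 member institutions, more than 43,000 providers" and adds that "there are about 456 Pulmonologist providing their patient data". On structure it says: "The data are organized by practice and provide longitudinal medical records for each patient".

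Section 9.3.1 gives the aim: "Since the purpose of this study is to identify predictors of IPF treatment initiation, no post-index follow-up measures will be reported". Sections 7 and 9.1 speak of characteristics that drive initiation, and section 9.7.1 uses p-values to help pick out the key drivers.

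Section 9.7.1 plans:
- **Standardized differences (ASDs):** the interval uses only the two cohort sizes and d. The decision rule is that "an ASD of at least 10% will be considered a meaningful difference".
- **Bivariate tests:** chi-square, Wilcoxon rank sum or t-test.
- **Secondary objective:** propensity scores and "multivariable logistic regression (possibly with stepwise selection) after controlling for key baseline characteristics", with covariates chosen on bivariate significance or face validity.
- **Significance level:** "Statistical tests will be two-sided, with α -level of 0.05 for statistical significance".

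No section mentions a practice or provider identifier, practice effects, a cluster-robust variance or a cluster bootstrap. Sections 9.9 (limitations) and 9.12 (bias) do not raise the issue. The nearest variables in section 9.3.3 are prescriber specialty (listed for the two treated cohorts only), region and payer type.

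**The concern.** This is a study of prescribing choice, and the prescriber makes that choice. A practice that favours one drug, or prescribes neither, passes its local case mix, payer mix and test-recording habits to one cohort. Two things follow.

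1. **Precision.** If treatment choice and a characteristic both vary between practices, patients in one practice carry overlapping information. The planned standard errors are then too small. The same p-values feed the bivariate screen that selects covariates for the logistic models.
2. **Interpretation.** A difference that exists only between practices has the same form in the ASD or odds ratio as one that operates between patients of the same practice. The planned analysis cannot tell them apart, yet the report is to name patient characteristics that drive initiation.

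A robust variance addresses the first point. It does not change a point estimate, so it leaves the second open.

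**Working it through.** **Inputs from the documents.** Cohort sizes come from the abstract: "A preliminary analysis identified 868 IPF patients with pirfenidone, 615 patients with nintedanib, and about 10,000 untreated patients". That gives 868 + 615 = 1,483 treated and about 11,483 in all. These are preliminary counts. More than 725 institutions and about 456 pulmonologists are totals for the whole database (section 9.4).

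**Assumed, because the documents give no value.** Number of contributing practices; variation in practice size; latent (probit) within-practice correlation of 0.2 for the characteristic and 0.3 for treatment choice; prevalence of the characteristic 30%.

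**Step 1: the plan's own precision.** The plan states no design effect or power, so there is no figure to reproduce. Its formula at d = 0.10, nintedanib vs pirfenidone:

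SE = sqrt[1,483/(615 × 868) + 0.10²/(2 × 1,483)] = 0.0527, so the 95% CI is 0.10 ± 0.103, or -0.003 to 0.203.

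**Step 2: average cluster size.** 1,483/725 = 2.0 treated patients per institution, or 1,483/456 = 3.3 per pulmonologist, if all contribute. For treated vs untreated, 11,483/725 = 15.8.

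**Step 3: inflation for a patient-level yes/no variable.** Convert each latent correlation r to the 0/1 scale: ICC = [Φ₂(z, z; r) − p²]/[p(1 − p)], with z the normal quantile of p. This gives 0.119 for the characteristic (p = 0.30), 0.192 for nintedanib vs pirfenidone (p = 615/1,483) and 0.142 for treated vs untreated (p = 1,483/11,483).

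Design effect DE = 1 + e × ICC(characteristic) × ICC(treatment), where e = (N − 1)/k × (1 + CV²) is the expected number of other patients in the same practice, k the number of practices and CV the variation in practice size. Actual two-sided error = 2[1 − Φ(1.96/√DE)].

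| Comparison | k | CV | e | DE | Error, formula | Error, simulated |
|---|---|---|---|---|---|---|
| Nintedanib vs pirfenidone | 725 | 0 | 2.04 | 1.05 | 5.5% | 5.6% |
| Same | 300 | 0 | 4.94 | 1.11 | 6.3% | 6.3% |
| Same | 150 | 0 | 9.88 | 1.23 | 7.7% | 7.5% |
| Same | 75 | 0 | 19.76 | 1.45 | 10.4% | 10.4% |
| Treated vs untreated | 725 | 0 | 15.84 | 1.27 | 8.2% | 8.3% |
| Same | 725 | 1 | 31.67 | 1.53 | 11.3% | 11.3% |

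The simulation used 40,000 replicates per row, probit practice effects and no patient-level association. These are unadjusted tests of one characteristic. They indicate the scale for the logistic models and do not reproduce them.

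**Step 4: no clustering of treatment choice.** With ICC(treatment) = 0 the product is zero and DE = 1, however strongly the characteristic clusters. Simulation gave 4.9% to 5.0%.

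**Step 5: a variable fixed within practice, such as region.** Its ICC is 1, so with an assumed correlation of drug choice of 0.15, DE = 1 + (m − 1) × 0.15. For m = 5, 10 and 20 patients per practice, DE = 1.60, 2.35 and 3.85, and the error is 12%, 20% and 32%. At the averages in step 2 (m = 2.05 and 3.25), DE = 1.16 and 1.34, and the error is 6.8% and 9.0%.

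**The case against.** The strongest case against has four parts.

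**The primary criterion does not depend on standard errors.** The 10% ASD threshold applies to a point estimate, and the primary objective is to describe and compare cohorts. A difference that arises between practices is still a real difference between those cohorts. This stands. The concern bears on the intervals, the p-values and the driver interpretation, not on the ASDs as description.

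**The inflation may be small.** If treated patients are spread thinly, nintedanib vs pirfenidone is almost unaffected. This also stands for that comparison. It does not carry over to treated vs untreated, where clusters average about 16 patients even over 725 institutions.

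**The prescriber is not wholly absent.** Specialty, region and payer type are collected, and face validity could bring them into a model. But specialty is not drug preference, it is not listed for the untreated cohort, and none of the three is a prespecified model term.

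**The practice identifier may not be available.** Section 9.4 suggests that it exists, but the list of analysis variables there names none and the files are de-identified. This stands, and the fix has to allow for it.

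Three stronger readings are tempting and not supported:
- A reader might infer that intervals are too narrow for every characteristic that clusters by practice. Step 4 shows that treatment choice must cluster too, and the documents give no evidence on how strongly it does.
- A reader might take 12% to 32% as the general error rate. Those figures hold only for practice-fixed variables at the assumed correlation and cluster sizes.
- A reader might take 725 as the number of practices behind the IPF cohorts. It counts institutions in the whole database; institution, practice and provider are different units.

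**Conclusion.** The omission is real and worth correcting. Every planned interval, test and model assumes independent patients in data grouped by practice, and no section acknowledges it. Where treatment choice and a characteristic both cluster, the stated precision is too good and a practice difference can be reported as a patient-level driver.

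The size is conditional. For patient-level variables under the assumed latent correlations of 0.2 and 0.3, the actual error of a 5% test is about 5-6% (725 practices) to 10% (75 practices) for nintedanib vs pirfenidone. It is about 8-11% for treated vs untreated over 725 practices, so that comparison is the more exposed. With no clustering of treatment choice it stays at 5%. The documents cannot place the study within this range. The sponsor can narrow it by counting practices and patients per practice, if the extract identifies practices.

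**What to change.** In section 9.7.1:
1. Define the cluster unit. Report the number of practices and the distribution of patients per practice, by cohort.
2. Use practice-level cluster-robust or cluster-bootstrap intervals and p-values for the ASDs, the accompanying bivariate tests and both logistic models.
3. Add, as a sensitivity analysis, a model that separates within-practice from between-practice association: either logistic regression conditional on practice, or a random intercept with practice means of the covariates. A random intercept alone is not enough, because its coefficient mixes the two associations.
4. Report the share of patients in practices that contribute both groups. In simulation under the assumptions above, about 51% of treated patients were in practices with both drugs at 725 practices, and 66% at 456. The within-practice estimate may therefore be imprecise. Use it to qualify the driver wording, not as a pass/fail rule, and do not apply it to practice-fixed variables such as region.

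In section 9.9: if the de-identified extract has no practice identifier, state this and describe the results as associations.

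**Cost.** Analysis wording and standard SAS procedures, with no new data if the identifier is present. Intervals become somewhat wider, and practices with only one group drop out of the conditional sensitivity model.
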